2.5.5 Additional efficacy analyses including PRO endpoints

All other exploratory efficacy endpoints will be summarized descriptively and analyzed using a similar method for the primary efficacy endpoint described in [Section 2.5.1](#). For PDSS/PDIS, following the scoring method and algorithm, results will be summarized by descriptive statistics, MMRM, and responder analysis. The analyses will be based on mITT population.

Analyses of efficacy data in extension treatment (ETP)

Unless otherwise specified, ETP efficacy analyses will use the mITT population, where patients will be considered to be in the treatment group to which they were randomized.

All efficacy endpoints will be summarized descriptively at each study visit, as well as the last observation available during the study. For study visits in ETP (beyond week 49), both changes from baseline and changes from ETP baseline (week 49) will be presented.

2.5.5.1 Analyses of efficacy data in ETP at PAP database lock

At PAP database lock, all available efficacy data for those patients who have entered ETP will be summarized descriptively. Graphical displays will be provided when appropriate.

Long-term effect of avalglucosidase alfa will be assessed among patients who receive avalglucosidase alfa throughout the blinded treatment phase, as well as the long-term follow-up phase. Descriptive statistics and graphical display will be provided to assess trend over time on all efficacy endpoints.

2.5.5.2 Analysis of the effect of switching from alglucosidase alfa to avalglucosidase alfa

Two analyses are planned to evaluate effect of avalglucosidase alfa in treatment experienced patients.

In the first analysis, a piecewise linear mixed effect model for % FVC (predicted) and 6MWT will be fitted for all patients who switched from alglucosidase alfa in PAP to avalglucosidase alfa in ETP. This analysis will be conducted to address a comment from CHMP in 2015. The model will include time as a continuous effect but assumed separate pre and post-switch slope for the time variable, with random intercept and slope at subject level. Similar piecewise linear model will be

generated for the patients in the avalglucosidase alfa arm who continue on the open label avalglucosidase alfa treatment. Model assumption on linearity of trend before and after 49 weeks will be assessed and the model maybe modified if there is good rational to justify an alternative model.

Due to potential period effect (patients may have FVC decline over time as the disease progresses), the estimated rate of change in % FVC (predicted) before and after switch may not be representative of the treatment effect of avalglucosidase alfa directly. The possibility of period effect will be assessed based on patients who were randomized to avalglucosidase alfa from study initiation without switching.

In order to support the label for the broader study population, an additional analysis will be conducted in % FVC (predicted) comparing the value from Week 49 to Week 97, by using a within-patient test in the treatment group who switched from alglucosidase alfa in PAP to avalglucosidase alfa in ETP. The change in % FVC (predicted) from Week 49 to Week 97 and the associated 95% CI will be calculated from the MMRM with fixed term for visit and random term for subject. This MMRM analysis will be based on % FVC (predicted) data from Week 49 and subsequent visits in ETP. Since database lock is planned once all data in PAP are observed, not all patients would have the week 97 visit by the cutoff date of PAP database lock. Thus, the majority of missing data at visits in ETP including Week 97 are expected to be attributable to an administrative reason that can be reasonably assumed missing at random. As explained by Brown and Prescott (28), within-subject correlations across the time points in MMRM allow observations at each time point to influence estimates of treatment effects at every other time point, and under missing at random MMRM improves efficiency than using the data from Week 49 and Week 97 visits only. In addition, summary statistics in % FVC (predicted) change from Week 49 will be provided by the randomized treatment groups at all ETP visits (including at Week 121) along with 95% CI for the within-subject comparison as appropriate. Summary statistics include the number of patients whose data are not missing, the sample mean with a 95% CI, the standard deviation, median, minimum, and maximum. The 95% CI at each visit will be constructed using only the data at that visit.

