1.3 DETERMINATION OF SAMPLE SIZE

Sample size calculations are based on non-inferiority test of the primary efficacy endpoint of change from baseline to Week 49 in FVC (% predicted) upright position, with the following assumptions:

Primary endpoint is normally distributed with a common standard deviation (SD) of 5.1% predicted, which is estimated based on the data from previous Phase 3, placebo-controlled LOTS trial (AGLU02704).

Mean treatment difference (avalglucosidase alfa–alglucosidase alfa) of 2.0% predicted, assumed based on a conservative estimate when comparing studies AGLU02704 and TDR12857 ([Section 1.3.2](#)).

A 2-sided 5% significance level,

Expected percent of missing data of up to 10% (estimated based on studies AGLU02704 and EMBASSY),

A non-inferiority margin of 1.1% predicted, which is based on the estimated alglucosidase alfa effect from the placebo-controlled study AGLU02704 ([Section 1.3.1](#)).

A total sample size of 96 (1:1 randomization ratio) will provide approximately 80% power to demonstrate non-inferiority of avalglucosidase alfa versus alglucosidase alfa, when the true treatment difference (avalglucosidase alfa–alglucosidase alfa) is 2.0% predicted. If the non-inferiority criterion is met, a test for superiority will be performed. If the true difference between avalglucosidase alfa and alglucosidase alfa is 3.6% predicted (see [Table 3](#)), the study will have more than 85% power to demonstrate superiority of avalglucosidase alfa to alglucosidase alfa.

Calculations were made using East 6.3 software.

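### The piecewise switch model in SAP 2.5.5.2 does not give patients separate random slopes before and after the switch; if one shared slope is fitted, the SE of the slope change is too small whenever patients respond differently to switching

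*SAP*

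**What the plan says.** SAP 2.5.5.2 plans two analyses of the switch. The first is a piecewise linear mixed model for FVC % predicted and 6MWT in patients who move from alglucosidase alfa to avalglucosidase alfa. Time is continuous, and the model "assumed separate pre and post-switch slope for the time variable, with random intercept and slope at subject level". Its stated purpose is regulatory: "This analysis will be conducted to address a comment from CHMP in 2015". A similar model is planned for the arm that stays on avalglucosidase alfa, and that arm is used to look for a period effect. Linearity before and after Week 49 will be checked, and "the model maybe modified if there is good rational to justify an alternative model". The SAP also cautions that "the estimated rate of change in % FVC (predicted) before and after switch may not be representative of the treatment effect".

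The section gives no program code, no covariance structure for the random effects and no rule for non-convergence. By contrast, the primary MMRM in SAP 2.5.1 has an unstructured covariance, an ordered list of fallbacks and SAS code.

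The second analysis is separate and covers FVC only: "The change in % FVC (predicted) from Week 49 to Week 97 and the associated 95% CI will be calculated from the MMRM".

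**The concern.** The quantity of interest in the first analysis is the change in slope at the switch. The fixed part allows the mean slope to change. If the random part holds a single slope over total time, each patient's deviation from the mean slope is the same before and after the switch and cancels in the difference. The model then treats every patient as having the same slope change. Patients may well differ in how they respond to a new enzyme, and that variation would be missing from the SE.

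The wording leans towards the single slope. The linear mixed model in SAP 2.5.3.2 (item 4) uses almost the same phrase for a model with one time slope, where it can only mean one random slope per patient.

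At stake is the apparent precision of the switch effect. For 6MWT this is the only model-based switch analysis in the section. The same gap would carry into the similar model for the continuing arm, and so into the judgement about a period effect.

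**Working it through.** **Inputs from the documents.** The design uses "A 2-sided 5% significance level" and an SD of change of 5.1 (SAP 1.3). There are 96 patients randomised 1:1, with 10% allowed for missing data. FVC visits are baseline and Weeks 13, 25, 37, 49, then 61, 73, 97, 121, 145 (Protocol 10.1.3.5 and 10.1.4.5).

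**The plan's own figure.** None is given for the switch model. The design power that uses the 5.1 does reproduce:
- 0.9 × 96 ≈ 86, or 43 per arm.
- SE = 5.1 × √(2/43) = 1.10, and (2.0 + 1.1)/1.10 = 2.82.
- Normal power is Φ(2.82 − 1.96) = 80.5%. The noncentral t gives 79.6%, as in SAP Table 4.

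This bears on the point only by supplying the 5.1.

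**Assumptions, not in the documents.**
- 44 switchers with all visits present (10% loss from 48 would leave 43).
- Time in years = (week − 1)/52, with the knot at Week 49 (48/52 = 0.923).
- Intercept SD 13; residual SD σ of 2.5 or 3.2.
- Pre-switch slope SD τ₁ set so that the Week 49 change has SD 5.1; post-switch slope SD τ₂ equal to τ₁ or half of it.
- Correlation ρ between a patient's two slopes of 0, 0.5 or 0.9.

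**Calibration.** 5.1² = 2σ² + τ₁² × 0.923².
- σ = 2.5: τ₁ = √(26.01 − 12.50)/0.923 = 3.98 per year.
- σ = 3.2: τ₁ = √(26.01 − 20.48)/0.923 = 2.55 per year.

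**Correct SE.** With complete visits, SE² = (σ²A + V)/n. Here V = τ₁² + τ₂² − 2ρτ₁τ₂ is the between-patient variance of the slope change. A = c′(X′X)⁻¹c for the contrast post minus pre, which is 5.10 for visits to Week 97 and 2.38 to Week 145.

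**One-slope SE.** V is forced to zero, so SE = σ̂√(A/n). The fitted residual SD σ̂ absorbs part of the lost variation. I took σ̂ from the best-fitting (minimum Kullback-Leibler) one-slope model.

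**Example** (Week 97, σ = 2.5, ρ = 0.5, equal slope SDs).
- Correct: √((6.25 × 5.10 + 15.86)/44) = 1.041, with V = 13.51/0.852 = 15.86.
- One slope: σ̂ = 2.60, so 2.60 × √(5.10/44) = 0.885.
- Ratio 0.885/1.041 = 0.85; coverage 2Φ(1.96 × 0.85) − 1 = 90.4%.

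**Range** (equal slope SDs; halving τ₂ stays inside these limits).

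| Data to | σ | ρ | One-slope SE | Correct SE | Ratio | Coverage |
|---|---|---|---|---|---|---|
| Week 97 | 2.5 | 0.9 | 0.858 | 0.892 | 0.96 | 94.1% |
| Week 97 | 2.5 | 0 | 0.919 | 1.202 | 0.76 | 86.6% |
| Week 97 | 3.2 | 0.9 | 1.091 | 1.103 | 0.99 | 94.8% |
| Week 97 | 3.2 | 0 | 1.111 | 1.217 | 0.91 | 92.7% |
| Week 145 | 2.5 | 0.9 | 0.589 | 0.640 | 0.92 | 92.9% |
| Week 145 | 2.5 | 0 | 0.654 | 1.029 | 0.64 | 78.7% |
| Week 145 | 3.2 | 0.9 | 0.746 | 0.763 | 0.98 | 94.5% |
| Week 145 | 3.2 | 0 | 0.768 | 0.921 | 0.83 | 89.8% |

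**Null check.** With ρ = 1 and equal slope SDs, V = 0. The two SEs agree (0.851 and 0.851 to Week 97) and coverage is 95%.

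**Simulation** (400 REML runs per case, 44 switchers, σ = 2.86, slope SD 2.95 per year). At ρ = 0 the one-slope model covered 90.0% (Week 97) and 89.8% (Week 145); two slopes covered 94.0% and 95.2%. At ρ = 0.5 the one-slope coverage was 93.2 to 93.5%. The Monte Carlo SE near 95% is √(0.95 × 0.05/400) = 1.1 points, so the ρ = 0.5 results alone are not clearly below nominal.

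**The case against.** Four points can fairly be made for the plan.

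- **The text does not prove a single random slope.** A reader might infer that the SAP definitely fits one. The same clause uses the singular for the two fixed slopes, so the singular settles nothing, and one random slope per segment is a possible reading. This stands. The concern is conditional on how the model is programmed, though two competent programmers could fit different models from this text.
- **No interval or test of the slope change is planned.** A reader might infer that a planned CI or p-value is wrong. The first analysis specifies neither; the 95% CIs in the section belong to the Week 49 to Week 97 MMRM and the visit summaries. This also stands. The point applies to any measure of precision that is reported, and a before/after comparison of slopes says little without one.
- **The loss may be small.** Avalglucosidase alfa is a modification of alglucosidase alfa, so a patient's two slopes are plausibly positively correlated. With high correlation or large residual error, coverage stays near 95%. A flat statement that the interval is too narrow is therefore not supported. Equally, residual SD 1.5 with zero correlation would take coverage to 73% (Week 97) or 63% (Week 145), but nothing in the documents supports that case over the others.
- **The model is supportive and may be changed.** Protocol 11.5 allocates no significance level after the PAP. The permission to modify the model follows the linearity check, however, and does not commit anyone to examine the random part.

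The content of the CHMP comment is not in the documents, so whether the model answers it cannot be judged.

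**Conclusion.** The point holds in conditional form. Read literally, and in line with SAP 2.5.3.2, the random part has one slope over both segments. Fitted that way, it understates the SE of the slope change whenever patients differ in their response to the switch. Under the assumed inputs the understatement is 1 to 24% with data to Week 97 (coverage 87 to 95%) and 2 to 36% to Week 145 (coverage 79 to 95%). It is zero if slope changes do not vary.

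These sizes rest on the assumed residual SD and slope correlation, on complete visits, and on FVC; nothing separate was computed for 6MWT. It would be wrong to infer that the main result is in doubt: the primary non-inferiority and superiority tests and the Week 49 to Week 97 comparison do not use this model. This is a minor point, worth correcting because the repair is cheap.

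**What to change.** State in SAP 2.5.5.2 that the model has a random intercept, a random pre-switch slope and a random post-switch slope (or, equivalently, a random slope change), with unstructured covariance and Kenward-Roger degrees of freedom. Name in advance a simpler structure for non-convergence that still keeps a separate random slope for each segment. Uncorrelated slopes would serve, although a zero correlation is itself a restriction and should be reported as such. Use the same structure for the continuing avalglucosidase alfa arm, and say whether an interval for the slope change will be reported.

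The cost is one or two sentences and a changed RANDOM statement. An unstructured 3 × 3 matrix has six parameters against three for a 2 × 2, so with about 44 patients there is some risk of non-convergence. That is why the fallback should be written down.

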2.6 ANALYSES OF SAFETY DATA

In PAP analysis, the safety analyses will be carried out with patients by the actual treatment received, irrespective of the treatment the patient has been randomized to.

- In ETP analysis and overall evaluation of avalglucosidase alfa safety, the safety analyses will be carried out by the following 4 groups:
- Group 1 includes data in PAP and ETP among subjects who received avalglucosidase alfa in PAP and ETP,
- Group 2 includes data in ETP among subjects who received alglucosidase alfa in PAP and received avalglucosidase alfa in ETP,
- Group 3 includes data in PAP and/or EPT among subjects who received avalglucosidase alfa in that period,

- Group 4 includes data in PAP and/or EPT among pediatric subjects who received avalglucosidase alfa in that period.

General rules

All safety analyses will be performed on the safety population as defined in [Section 2.3.2](#), unless otherwise specified, using the following common rules:

- The baseline value is the last available value before the start of first infusion in PAP or ETP, except possibly ECG parameters. The complete definitions of baseline are listed in [Section 2.1.1](#).
- The potentially clinically significant abnormality (PCSA) values are defined as abnormal values considered medically important by the Sponsor according to predefined criteria/thresholds based on literature review and defined by the Sponsor for clinical laboratory tests, vital signs, and ECG (PCSA version dated May 2014 [[Appendix A](#)]).
 - PCSA criteria will determine which patients had at least 1 PCSA during the treatment epoch, taking into account all evaluations performed during the period, including nonscheduled or repeated evaluations.
 - The number of all such patients will be the numerator for the on-treatment PCSA percentage; the denominator will be the number of patients assessed for that given parameter in the treatment epoch in the safety population.
- The analysis of the safety variables will be essentially descriptive and no inferential testing is planned.

2.6.1 Analyses of adverse events

Generalities

The primary focus of adverse event reporting will be on treatment-emergent adverse events. Pretreatment and posttreatment adverse events will be described separately.

If an adverse event date/time of onset (occurrence, worsening, or becoming serious) is incomplete, an imputation algorithm will be used to classify the adverse event as pretreatment, treatment-emergent, or post-treatment. The algorithm for imputing date/time of onset will be conservative and will classify an adverse event as treatment-emergent unless there is definitive information to determine it is pretreatment or post-treatment. Details on classification of adverse events with missing or partial onset dates are provided in [Section 2.10.3](#).

Adverse event summaries will include number (n) and percentage (%) of patients experiencing an adverse event. The denominator for computation of percentages is the number of patients in the specific population within each treatment group. The number of events will be included in some summaries as well whenever appropriate.

Unless otherwise specified, sorting order will follow the internationally agreed SOC order, and further by decreasing number of events in PTs within SOCs in avalglucosidase alfa arm. When

more than one PT has same number of events, the order of presentation will be alphabetical in PTs.

Multiple occurrences of the same event in the same patient will be counted only once in the tables within a treatment phase.

Analysis of all treatment-emergent adverse events in PAP

The following treatment-emergent adverse event summaries will be generated for the safety population.

- An overview of treatment-emergent adverse events in PAP. Number (%) of patients will be provided by treatment group to include:
 - Treatment-emergent adverse events,
 - Serious treatment-emergent adverse events,
 - Treatment-emergent adverse events related to study drug,
 - Protocol-defined IARs,
 - Algorithm-defined IARs,
 - Treatment-emergent adverse events leading to death,
 - Treatment-emergent adverse events leading to permanent treatment discontinuation.
- All treatment-emergent adverse events during PAP by primary SOC, HLG, HLT, and PT, showing number (%) of patients with at least 1 treatment-emergent adverse event sorted by the SOC internationally agreed order. The other levels (HLG, HLT, PT) will be presented in alphabetical order.
- All treatment-emergent adverse events during PAP by primary SOC and PT sorted by the internationally agreed SOC order and by decreasing incidence of PTs within each SOC for the avalglucosidase alfa arm.
- All treatment-emergent adverse events during PAP presented by PT, sorted by decreasing incidence of PT in the avalglucosidase alfa arm.
- All treatment-emergent adverse events regardless of relationship during PAP by primary SOC, and PT,
- All treatment-emergent adverse events during PAP by maximal severity (ie, mild, moderate, or severe), presented by primary SOC and PT,
- Most common treatment-emergent adverse events during PAP by primary SOC and PT sorted by the internationally agreed SOC order and by decreasing incidence of PTs within each SOC for the avalglucosidase alfa arm. The most frequent TEAE are defined as those preferred terms with incidence of $\geq 5\%$ in the avalglucosidase alfa treatment arm.
- Treatment-emergent adverse events with potential difference between treatment arms during PAP, by primary SOC and PT. The events with potential difference are defined as those preferred terms with difference in incidence rate of $>10\%$ between arms.

- For group 3 only, number (% per 1 year) of patients experiencing TEAEs by time of onset will be presented by SOC and PT.

Analysis of all treatment emergent serious adverse event(s) in PAP

- All treatment-emergent SAEs during PAP by primary SOC, and PT,
- All treatment-emergent SAEs regardless of relationship and related to IMP during PAP, by primary SOC, and PT.
- SAE listings will be provided as well.

Analysis of all treatment-emergent adverse event(s) leading to treatment discontinuation in PAP

- Treatment-emergent adverse events leading to treatment discontinuation during PAP, by primary SOC and PT,
- Treatment-emergent adverse events leading to treatment discontinuation during PAP presented by PT, sorted by decreasing incidence of PT in the avalglucosidase alfa arm,
- Listing of treatment-emergent adverse events leading to treatment discontinuation during PAP, including details on dose, severity, relationship, and outcome, etc.

Analysis of adverse events with AESIs in PAP

- Treatment emergent AESIs during PAP, by primary SOC and PT, showing the number (%) of patients, sorted by decreasing incidence of PT within the avalglucosidase alfa arm,
- Treatment emergent protocol-defined IARs during PAP, by primary SOC and PT, presented by overall number (%), as well as by start time of IAR in relation to infusion time (0-3 hrs, >3-24, >24-72, >72 hrs),
- Treatment emergent algorithm-defined IARs during PAP, by primary SOC and PT, presented by overall number (%), as well as by start time of IAR in relation to infusion time (0-3 hrs, >3-24, >24-72, >72 hrs),
- Treatment emergent protocol-defined IARs during PAP, by PT and worst severity, presented by overall number (%), as well as by start time of IAR in relation to infusion time (0-3 hrs, >3-24, >24-72, >72 hrs),
- Treatment emergent algorithm-defined IARs during PAP, by PT and worst severity, showing presented by overall number (%), as well as by start time of IAR in relation to infusion time (0-3 hrs, >3-24, >24-72, >72 hrs).

Analysis of all treatment-emergent adverse events in ETP

Similar analyses of the adverse events will be performed for the ETP as the PAP.

In addition, overall analysis of adverse events for the patients who receive avalglucosidase alfa, will be performed.

Analysis of pretreatment and post-treatment adverse events

- All pretreatment adverse events by primary SOC and PT,
- All adverse events with onset during the post treatment period of PAP or ETP by primary SOC and PT,
- All posttreatment SAEs with onset during the post treatment period of PAP or ETP by primary SOC and PT.

Anaphylactic/hypersensitivity reactions and immune-mediated reactions

A comprehensive programming search of AEs which meet the Standard MedDRA Query (SMQ) criteria for hypersensitivity and anaphylactic reaction will be used to identify adverse events that potentially are associated with symptoms of anaphylactic and hypersensitivity reaction. Results of this search will be provided in summary tables and in a by patient listing by group. The most recent version of MedDRA SMQ will be used at the time of analysis. A medical review of these cases will be performed.

A listing of potential immune mediated reactions will be provided. Search criteria will include but not limited to the MedDRA Preferred Terms of glomerulonephritis, nephrotic syndrome, proteinuria, hematuria, vasculitis, serositis, myocarditis, skin lesion, skin necrosis, arthralgia, arthritis, myalgia, arthropathy, lymphadenopathy, serum sickness, type III immune complex mediated reaction and influenza-like symptoms. A medical review of these cases will be performed.

The exposure adjusted incidence rate (EAIR) for selected TEAEs will be calculated as number of patients with the specific TEAEs divided by patient years. For the calculation of EAIR, for patients with event, the patient year is calculated as time from first treatment infusion to the time of first event; for patients without event, it is calculated as time from first treatment infusion to the last administration + 4 weeks (28 days). The rate per 100 patient years will be displayed for all the categories described below.

The EAIRs will be calculated for the following TEAEs:

- Overview of TEAEs (Including patients with any TEAE, patients with any treatment-emergent SAE, patients with any TEAE potentially related to avalglucosidase alfa, patients with any treatment-emergent severe AE, patients with any TEAE leading to death, patients with any TEAE leading to permanent treatment discontinuation). SOC and PT will not be displayed in this table;
- TEAEs by primary SOC and PT.

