2.4 STATISTICAL METHODS

Unless otherwise specified, efficacy analyses will use the mITT population, where patients will be considered to be in the treatment group to which they were randomized. Corresponding supportive analysis will be performed for PP population as well. Safety analyses will use the safety population, where patients who receive at least one infusion of avalu glucosidase alfa in PAP will be assigned to the avalu glucosidase alfa arm for the PAP safety analysis purposes.

For all analyses, the avalu glucosidase alfa treatment group will be compared to the alglucosidase alfa group. While the primary comparison of interest is at 12 months (49 weeks), all summary statistics will be computed and displayed by treatment group and each scheduled assessment time as well. Summary statistics for continuous variables will minimally include n, mean, SD, minimum, median, and maximum. For categorical variables, frequencies and percentages will be presented. Graphical displays will be provided as appropriate.

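### The most-frequent-TEAE table picks its rows on the avalglucosidase alfa arm alone, which tilts low-rate terms against that arm and omits terms frequent only on alglucosidase alfa; an either-arm rule removes both effects

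*SAP*

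**What the plan says.** Among the tables for the primary analysis period (PAP), SAP 2.6.1 lists the most common treatment-emergent adverse events by system organ class and preferred term. The entry rule reads: "The most frequent TEAE are defined as those preferred terms with incidence of" at least 5% "in the avalglucosidase alfa treatment arm". No condition refers to alglucosidase alfa.

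The table is a two-arm display. SAP 2.4 states that the two groups are compared in all analyses and that "all summary statistics will be computed and displayed by treatment group and each scheduled assessment time as well".

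Three other provisions bear on the point:

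- **Tables with no frequency threshold.** SAP 2.6.1 plans "All treatment-emergent adverse events during PAP by primary SOC and PT sorted by the internationally agreed SOC order" and "All treatment-emergent adverse events during PAP presented by PT, sorted by decreasing incidence of PT in the avalglucosidase alfa arm". In the second, the test arm sets only the order of the rows. Tables through the full MedDRA hierarchy and by maximal severity also have no threshold.
- **A second selected table.** It covers events that may differ between arms: "The events with potential difference are defined as those preferred terms with difference in incidence rate of" more than 10%. No direction is given.
- **Status.** SAP 2.6 says: "The analysis of the safety variables will be essentially descriptive and no inferential testing is planned".

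**The concern.** When rows are admitted on one arm's observed count, that arm's column contains chance highs by construction, while the other column is an ordinary unselected estimate. Set side by side, the two show a gap that comes partly from the entry rule. The effect is strongest for terms whose true rate is near or below the threshold, and with arms of about 48 the threshold is only 3 patients.

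The second consequence is omission. A term seen often on alglucosidase alfa and rarely on avalglucosidase alfa does not enter the table, although it is part of a head-to-head safety comparison. At stake is the neutrality of one condensed safety table in a randomised double-blind trial.

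**Working it through.** **Inputs.** SAP 1.3 gives the total and the allocation: "A total sample size of 96 (1:1 randomization ratio) will provide approximately 80% power". The thresholds, 5% on the test arm and a difference above 10%, are in SAP 2.6.1. Neither document gives preferred-term rates, so every rate below is an assumption. I take 96/2 = 48 treated patients per arm, with counts independent between arms.

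**Checking the arm size.** With SD 5.1, a distance to the margin of 2.0 + 1.1 = 3.1 and two-sided 5%, the number per arm is 2 × (1.960 + 0.842)² × 5.1² / 3.1² = 42.5, so 43. Allowing 10% missing, 86/0.9 = 95.6, so 96. Power by the t distribution at 43 per arm is 79.6%, as in SAP Table 4. The arm size is not in dispute.

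**Thresholds in patients.** 2/48 = 4.2% fails the 5% rule and 3/48 = 6.25% passes, so a term is listed when the test count X is at least 3. A difference above 10% needs more than 4.8 patients, so at least 5.

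**Selection effect with equal true rate p.** X is Binomial(48, p).

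- Probability of listing: P(X ≥ 3) = 1 − P(0) − P(1) − P(2).
- Mean displayed test rate when listed: [48p − P(1) − 2P(2)] / [48 × P(X ≥ 3)].
- The comparator mean stays at p, because its count is independent of the selection.

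For p = 5%: P(0) = 0.0853, P(1) = 0.2154 and P(2) = 0.2664, so P(X ≥ 3) = 0.433. The mean count when listed is (2.4 − 0.2154 − 0.5328)/0.433 = 3.815, and 3.815/48 = 8.0%.

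| True rate, both arms | P(listed) | Mean shown, test vs comparator | Excess (points) |
|---|---|---|---|
| 3% | 0.17 | 7.1% vs 3.0% | 4.1 |
| 4% | 0.30 | 7.5% vs 4.0% | 3.5 |
| 5% | 0.43 | 8.0% vs 5.0% | 3.0 |
| 10% | 0.87 | 11.0% vs 10.0% | 1.0 |
| 15% | 0.98 | 15.2% vs 15.0% | 0.2 |
| 20% | 1.00 | 20.0% vs 20.0% | about 0 |

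**Omission with a true comparator excess.** Take 2% on test and 10% on comparator. The term is at 5% or more on the comparator and below 5% on test with probability 0.81. To miss the difference table as well, the gap must be 4 patients or fewer. That leaves test 0 with comparator 3 or 4, test 1 with 3 to 5, and test 2 with 3 to 6. The test probabilities for 0, 1 and 2 are 0.379, 0.371 and 0.178. The comparator probabilities for 3, 4, 5 and 6 are 0.151, 0.189, 0.185 and 0.147.

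0.379 × 0.340 + 0.371 × 0.524 + 0.178 × 0.671 = 0.129 + 0.195 + 0.119 = 0.44

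The same sum at 2% vs 12% gives 0.35. The largest observed imbalances that miss both selected tables are 4/48 (8.3%) against 0, 5/48 (10.4%) against 1 and 6/48 (12.5%) against 2.

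**Under an either-arm rule.** With equal true rates the selection is symmetric, so both arms have the same expected listed rate: 4.9% each at p = 3%, 6.1% each at 5% and 10.1% each at 10%. The selection difference is zero.

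**The case against.** The strongest reply is that this table is meant to describe what is common on the new product, and that the comparison is made elsewhere. Much of that stands. The unthresholded tables show every preferred term by arm, so a reader who infers that comparator events are hidden from the safety report would be wrong: they are missing only from this table. The documents also give no support for the idea that readers will use the condensed table instead of the full ones.

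The difference table also matters. At true rates of 2% and 12%, a term enters the most-common table with probability 0.07 as written and 0.94 under an either-arm rule. Quoted alone, that contrast overstates the loss, because the difference table catches the term with probability 0.54, and at least one of the two selected tables shows it with probability 0.59.

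A reader might also suspect a presentation that favours the sponsor. The direction is the opposite: low-rate terms look worse on avalglucosidase alfa, and terms on which it does better drop out. Nor does the table assert an excess, since no testing is planned.

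What the reply does not remove is the tilt within the table itself, or the moderate comparator excesses that miss both selected tables. A direction unfavourable to the test drug does not make the display neutral.

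**Conclusion.** The one-arm entry rule is in the text and has two measurable effects on this table. It raises the displayed test-arm rate of low-rate terms, by 3 to 4 points for true rates of 3% to 5%, about 1 point at 10%, and negligibly from about 15%. It also omits terms frequent only on alglucosidase alfa, some of which the difference table does not recover (probability about 0.44 at 2% vs 10%). The sizes rest on 48 treated patients per arm, independent counts and assumed rates. No hypothesis test, efficacy result or claim is affected, and nothing is lost from the full tables. This is a minor improvement in presentation.

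**What to change.** In SAP 2.6.1, define the most frequent TEAEs for the PAP as preferred terms with an incidence of at least 5% in either treatment arm. State that both arms are shown, and keep the order by decreasing incidence on avalglucosidase alfa. The cost is one phrase in the SAP and a somewhat longer table: at a true rate of 5% in both arms, for example, the probability that a term is listed rises from 0.43 to 1 − (1 − 0.433)² = 0.68. No new data or significance level is involved.
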